7.2 Study Endpoint(s)

Efficacy:

1. *leva* device angle measurements
2. Survey evaluations of incontinence including:
 - a. Urinary Incontinence Distress Inventory (UDI-6)
 - b. Incontinence Impact Questionnaire (IIQ-7)
 - c. Patient's Global Impression of Severity (PGI-S)
 - d. Revised Urinary Incontinence Scale (RUIS)
 - e. Patient's Global Impression of Improvement (PGI-I)
 - f. Clinician's Global Impression of Improvement (CGI-I)
 - g. Voiding diary

Safety and Tolerability:

1. Reported Adverse Events (AEs) and Serious Adverse Events (SAEs)

8 INVESTIGATIONAL PLAN

8.1 Overall Study Design and Plan

An open-label study in adult women with urinary incontinence.

Screening of subjects will occur in one to two visits to determine study eligibility.

Up to 25 subjects meeting inclusion/exclusion criteria at screening will participate in 6 (up to 8 weeks) of twice daily training sessions using the *leva* device. Subjects will be allowed up to 8 weeks to complete the study to accommodate scheduling issues, menstrual periods or planned vacations.

Training sessions last 2.5 minutes with alternating 15 seconds of voluntary contraction of the pelvic floor muscles and 15 seconds of rest.

Changes in urinary incontinence will be assessed by symptoms of incontinence, *leva* angle measurements and patient's and clinician's assessment of global improvement over the study period.

All subjects enrolled in the study will be asked to complete the FSFI and PISQ-IR surveys upon enrollment and at study end. Completion of the FSFI and PISQ-IR is optional, and completed surveys will be returned in a sealed envelope and reviewed following study completion.

All subjects who complete this study will be invited to participate in an optional interview with the Study Director and a marketing professional to better understand their experiences using the device. The interview will last up to one hour at the final visit.

8.1.1 Confinement and Return Visits

The screening visit may take up to 1 hour and the return visits will last about 15 minutes. See Study Events Flow Chart ([Section 4](#)).

For each visit, the subjects will report to the clinic at the time indicated by the Clinical Research Unit (CRU) and remain confined until completion of the training/testing with the female *leva* Trainer who is a licensed healthcare professional.

At the discretion of study staff, a female *leva* Trainer therapist may be sent to a subject's home for training/testing. There will be no additional charge for an at-home visit.

There are no overnight stays required for this study. At all times, a subject may be required to remain at the CRU for longer at the discretion of the Principal Investigator (PI).

8.2 Risks and/or Benefits to Subjects

leva Incontinence System™ is an FDA-approved Class II medical device. As such it has been tested and found to conform with the requirements of IEC 60601-1:2005 (3RD Edition), Medical Electrical Equipment-Part 1: General requirements for basic safety and essential performance; IEC 60601-1-2:2007, Medical electrical equipment-Part1-2:General requirements for basic safety and essential performance-Collateral standard: Electromagnetic compatibility-Requirements and tests; and IEC 60601-1-1-11, General requirements for basic safety and essential performance-Collateral standard: Requirements

for medical electrical equipment and medical electrical systems used in the home healthcare environment. The results of these tests indicate that the device is safe for its intended use. In addition, a biocompatibility evaluation was performed to satisfy ISO 10993-1 and FDA requirements. All patient contacting materials have been tested, and passed cytotoxicity, sensitization and irritation or intra-cutaneous standards. leva poses little to no risk to the patient if used as instructed.

The risks of use of the leva device are minimal to none however, there may be some unknown or infrequent or unforeseeable risks associated with the use of the device. The potential risks may include embarrassment with use of the intravaginal device; however the use of this should not conceptually differ from use of a tampon. Risks of course will be monitored throughout the entirety of the study.

8.3 Selection of Study Population

8.3.1 Inclusion Criteria

Subjects must fulfill all of the following inclusion criteria to be eligible for participation in the study, unless otherwise specified:

1. Subjects must be female.
2. Subjects must be capable of giving informed consent.
3. Subjects should be between at least 18 years of age.
4. Subjects must have a diagnosis of or symptoms of predominant mild to moderate urinary incontinence based on the results of the completed urinary incontinence surveys.

8.3.2 Exclusion Criteria

Subjects must not be enrolled in the study if they meet any of the following criteria:

1. Absence of a vagina.
2. Positive drug or alcohol test at the Screening visit.
3. Post-menopausal defined as absence of a period for over 12 months.
4. Pregnancy or being less than 12 months post-partum.
5. Greater than 3 vaginal deliveries or prior operative delivery (e.g. use of vacuum, forceps or abdominal pressure).
6. Symptoms of stage II or greater pelvic organ prolapse.
7. BMI >31 kg/m².
8. Diagnosis of any neurological disorder.
9. Prior lower back or pelvic surgery, including prior surgery for SUI.

10. Prior pelvic radiation.
11. Current or recurrent vaginal infections (>3 per year).
12. Painful bladder syndrome, active or chronic pelvic pain.
13. Concurrent PFME under a supervised therapeutic plan of care.
14. Previous supervised pelvic floor muscles rehabilitation in the past 12 months for the treatment for urinary incontinence or any other pelvic floor disorder.
15. Currently taking medication to treat incontinence.
16. Impaired cognitive function.
17. Unable to tolerate use of the *leva* vaginal device.

8.3.3 Removal of Subjects from the Study

Subjects are free to withdraw from the study at any time for any reason.

In addition, subjects may be withdrawn from the study by the PI in consultation with the Sponsor for the following reasons:

- Subject is unable to use the *leva* device;
- Subject experiences a SAE;
- Protocol violation.

The clinical report will include reasons for subject withdrawals.

8.3.4 Prohibitions and Concomitant Therapy

There are no prohibited therapies, activities or medications except as described in the exclusion criteria. All medications taken by subjects during the course of the study will be recorded.

8.3.5 Meals

Due to the short duration of confinement for each study period, subjects will not be provided with a meal.

8.3.6 Activity

The subjects will be required to remain standing while performing training and in weekly tests using the *leva* device. The subjects are allowed to be ambulatory (i.e., no restrictions for standing, walking, sitting, or lying down) at all other times.

8.4 Treatments

8.4.1 Treatment Administered

Subjects will train twice daily for 6 (up to 8 weeks) using the *leva* device. The female *leva* Trainer will assist the subject five days a week with the training session by helping to assure that the subject is performing the training using the correct muscle movements.

8.4.2 Treatment Compliance

The *leva* device retains results from the subject's previous training sessions. Therefore, when the subject trains at home or when a session is missed the female *leva* Trainer will be able aware of the data and can counsel the subject if no session data is recorded due to a missed session.

9 STUDY PROCEDURES

The Study Events Flow Chart ([Section 4](#)) summarizes the procedures to be performed at each visit. Individual procedures are described in detail below. Additional evaluations/testing may be deemed necessary by the PI and/or the Sponsor for reasons related to subject safety.

Any nonscheduled procedures required for urgent evaluation of safety concerns take precedence over all routine scheduled procedures.

Screening visit:

This visit may be conducted in one to two visits, as needed. The study will be explained by the Study Director and the consent will be reviewed with prospective participants. The consent will be obtained by the licensed Physician Investigator or his Study Director. The study participation will be entirely voluntary.

Each subject will provide samples for drug screening, pregnancy testing, and buccal swabs for alcohol screening.

The following surveys will be administered:

- Medical, Epidemiologic and Social Aspects of Aging (MESA)
- Urinary Distress Inventory questionnaire, short version (UDI-6)
- Incontinence Impact Questionnaire, short form (IIQ-7)
- Patient Global Impression of Severity (PGI-S) Scale
- Revised Urinary Incontinence Scale (RUIS)
- Voiding diary – 24 hours intake and output and symptoms diary - to be taken home and completed within the first week of participation
- Female Sexual Function Index (FSFI) (optional)
- Pelvic Organ Prolapse/Incontinence Sexual Questionnaire (PISQ-IR) (optional)

Medical History will be obtained to include:

- Demographic data
- Height/weight
- Concomitant medication
- Latex allergy (for selection of disposable probe cover)

The female *leva* Trainer therapist will familiarize the subject with the *leva* Incontinence System™ and instruct on the technique of contraction.

The female *leva* Trainer will conduct baseline *leva* testing and measurements will include: Baseline angle; angle with Valsalva (or bear down maneuver); highest angle with pelvic floor muscles contraction; ability to sustain contraction and contractions in timed 15 seconds. This series is called the *leva* Test.

The subject will train for 2 ½ minutes using the *leva* device (*leva* Training) – each cycle will have 15 seconds of contraction with 15 seconds of relaxation. Participants will perform 5 alternating repetitions.

The female *leva* Trainer will record *leva* device measurements.

Study visits 2-30 (with the female leva Trainer):

Frequency: once a day 5 days a week. The female leva Trainer will supervise the participants on performing 2 1/2 minutes of 5 repetitions of pelvic floor exercises using the leva Incontinence System TM (leva Training)

Once a week, preferably Mondays, during the about 6-8 week study period:

The subjects will be asked to perform a series of 5 exercises “leva Test” to test the effect of the daily training and follow the test with the 2 ½ minutes of training (leva Training). The female leva Trainer will record leva device measurements.

The study participants will be given the following surveys:

- UDI-6
- IIQ-7
- PGI-S
- RUIS

At 3 weeks:

The subjects will be asked to perform a series of 5 exercises (leva Test) to test the effect of the daily training and follow the test with the 2 ½ minutes of training (leva Training). The female leva Trainer will record leva device measurements.

The study participants will be given the following questionnaires:

- UDI-6
- IIQ-7
- PGI-S
- PGI-I
- RUIS
- Voiding diary completion

The Study Director or PI will complete the Clinician’s Global Impression of Improvement (CGI-I) evaluation.

At 6 weeks:

The subjects will be asked to perform a series of 5 exercises (leva Test) to test the effect of the daily training and follow the test with the 2 ½ minutes of training (leva Training). The female leva Trainer will record leva device measurements.

The study participants will be given the following questionnaires:

- UDI-6
- IIQ-7
- PGI-S
- PGI-I
- RUIS

The Study Director or PI will complete the Clinician’s Global Impression of Improvement

(CGI-I) evaluation.

At the End of Study/ Early Termination visit:

The subjects will be asked to perform a series of 5 exercises (*leva* Test) to test the effect of the daily training. The female *leva* Trainer will record *leva* device measurements.

The study participants will be given the following questionnaires:

- UDI-6
- IIQ-7
- PGI-S
- PGI-I
- RUIS
- Voiding diary completion
- FSFI (optional)
- PISQ-IR (optional)

The Study Director or PI will complete the Clinician's Global Impression of Improvement (CGI-I) evaluation.

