10.1.1 Determination of Sample Size

This is an open-label study where subjects serve as their own control. The sample size was selected without statistical considerations.

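### The voiding diary's only stated window is one 24-hour day, so leak counts from it would be imprecise and floor-limited; three days would help at small cost.

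*Combined protocol and SAP*

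**What the plan says.** - Section 7.2 includes "g. Voiding diary" among the efficacy endpoints, next to device angles, questionnaires and global ratings. No endpoint is named primary, and no diary variable (leaks, voids, volumes) is defined.
- Section 9, under the Screening visit, describes a "24 hours intake and output and symptoms diary", "to be taken home and completed within the first week of participation".
- The flow chart in Section 4 schedules the diary at Screen, Week 3 and End of Study, and not at Week 6. For the two later time points Section 9 says only "Voiding diary completion", with no length.
- Section 8.3.1, criterion 4, admits women with "predominant mild to moderate urinary incontinence based on the results of the completed urinary incontinence surveys". It sets no minimum leak count and no diary threshold.
- Section 8.1 sets the size: "Up to 25 subjects meeting inclusion/exclusion criteria at screening will participate". Section 10.1.1 adds: "This is an open-label study where subjects serve as their own control". The baseline diary is therefore the only comparator for the later ones.
- Section 10.1 leaves the methods to the Clinical Study Report, so the plan has no rule for a woman with no leaks at baseline.

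**The concern.** A woman with mild incontinence who leaks a few times a week will often have a dry day. If that is her diary day at baseline, her leak count can stay at zero or rise, but it cannot fall. For a woman who does leak that day, one day before and one day after estimate her usual frequency poorly. Both effects matter more with at most 25 women and no control group.

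The diary is also the only listed efficacy measure that logs symptoms over a defined day; the others are device angles, questionnaires and global ratings. What is at stake is the precision of that one endpoint. A real fall in leaks could be missed on the diary, and a single unusual day could move a small-sample mean in either direction.

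**Working it through.** The plan states no power, effect size, SD or leak rate, so it has no figure of its own to reproduce.

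**Inputs from the documents:** a 24-hour diary (Section 9, Screening); up to 25 women (8.1); within-subject comparison (10.1.1).

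**Assumptions:** leak rates of 1 to 21 per week, with leaks following a Poisson process. As a sensitivity check, rates vary between women (gamma, shape 1).

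**Step 1: chance of no leak.** With *w* leaks per week and *d* diary days, P(0) = exp(−*wd*/7) for a common rate, or 1/(1 + *wd*/7) for varying rates. For example, at 3 per week, one day gives exp(−3/7) = 0.651 and three days give exp(−9/7) = 0.276.

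| Leaks/week | 1 day, common rate | Expected zeros of 25 | 3 days, common rate | 1 day, varying rates | 3 days, varying rates |
|---|---|---|---|---|---|
| 1 | 87% | 21.7 | 65% | 88% | 70% |
| 2 | 75% | 18.8 | 42% | 78% | 54% |
| 3 | 65% | 16.3 | 28% | 70% | 44% |
| 7 | 37% | 9.2 | 5% | 50% | 25% |
| 14 | 14% | 3.4 | 0.2% | 33% | 14% |
| 21 | 5% | 1.2 | <0.1% | 25% | 10% |

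**Step 2: sampling noise within a woman.** The SD of a one-day count is √λ, where λ = *w*/7. The SD of a three-day mean is √(λ/3). The ratio is 1/√3 = 0.577, a cut of about 42% if days are independent. Positive correlation between days would make the gain smaller.

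**Step 3: effect on a group comparison.** Take an assumed 50% fall, 25 women and a common rate.

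- At 3 per week the mean fall is 0.4286 − 0.2143 = 0.2143 leaks per day.
- With one day, the variance of the change is 0.4286 + 0.2143 = 0.6429, so SE = √(0.6429/25) = 0.160 and the fall is 1.34 SE.
- With three days, SE = 0.160 × 0.577 = 0.093 and the fall is 2.31 SE.

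Simulation of a paired t-test (two-sided 5%, 10,000 runs) agrees. Power is shown as common rate / varying rates:

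| Leaks/week | 1 day | 3 days |
|---|---|---|
| 2 | 18% / 16% | 44% / 40% |
| 3 | 25% / 22% | 61% / 55% |
| 7 | 50% / 46% | 93% / 88% |
| 14 | 80% / 73% | 99.9% / 98.7% |

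The test and the 50% fall are illustrative; the plan specifies neither.

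**The case against.** Several objections stand and limit the point.

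- **A reader might infer that the diary cannot show improvement, or cannot support the objective.** The documents do not support that. A zero baseline limits an individual woman's leak count, but the group mean can still fall. One-day power for a halving is low at low rates, yet reaches 73% to 80% at 14 leaks per week. Symptoms are also measured weekly by UDI-6, IIQ-7, PGI-S and RUIS, and by two global ratings of improvement.
- **The share of dry baselines depends on a rate the protocol does not give.** Mild to moderate is not defined as a frequency. At 14 and 21 leaks per week with a common rate, only 14% and 5% would record none.
- **A reader might infer a bias towards improvement from one bad baseline day.** Entry is by survey, so the diary day is not selected for being bad. Single-day sampling adds noise in both directions.
- **The diary also records intake and output.** The floor calculation applies to leaks only.
- **The 24-hour length at the later time points is an inference**, though no other length appears.
- **A reader might infer that the final diary could never be collected**, because it is listed among items given at the last visit. The word completion fits handing in a diary issued before that visit equally well. This is an ambiguity of wording.
- **Three days is not a full cure.** At 1 and 2 leaks per week, 65% and 42% would still record none. Diary length also leaves a separate matter open: the first diary may be filled in during the first week, although training starts at Screening.

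None of this answers the loss of precision from using one day.

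**Conclusion.** The point holds in a limited form. The only stated diary window is 24 hours, in a population with no minimum leak frequency. If that window applies at all three time points, leak counts will be imprecise, and at assumed rates up to about one leak a day between 37% and 88% of women would start at zero. At two to three leaks a day the problem is small if women share a common rate (14% to 5%), and larger if rates vary (33% to 25%).

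The size rests on assumed leak rates and a Poisson model, and the 42% gain rests on independent days. The weakness affects one of several endpoints and does not threaten the study as a whole. It is worth correcting because the correction is cheap.

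**What to change.** In Section 9, specify a diary over three consecutive days at Screen, Week 3 and End of Study, and state that length at each time point. Summarise leaks as the mean per day, reported alongside the intake and output data.

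State that the Week 3 and final diaries are handed out at an earlier training visit, in time for three full days, and collected at the scheduled visit. Subjects already attend five days a week and training visits run to Visit 30, so no visit is added. Accept that women who stop early without warning may return fewer days.

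The cost is two more diary days at each of three time points: 2 × 3 = 6 per subject, or at most 6 × 25 = 150 in all, plus a few lines of text.

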3 SYNOPSIS

Device:	/leva Incontinence System™
Clinical Indication:	Urinary Incontinence
Study Objective:	The objective of this study is to assess the effectiveness of the /leva Incontinence System™ in treating bladder incontinence.
Summary of Study Design:	
An open-label study.
 
Screening of subjects will occur over 1-2 study visits to determine study eligibility.
 
Up to 25 subjects meeting inclusion/exclusion criteria at Screening will complete about 6-8 weeks of training and testing with a device to improve the strength of their pelvic floor muscles.
 
Weekly during the study the subjects will complete tests using the /leva device to assess changes in their pelvic floor muscle strength. Subjects will also complete surveys to assess improvements in the symptoms of their urinary incontinence.
 
The FSFI and PISQ-IR surveys will be provided to subjects to complete at the Screening visit and upon study completion and will be returned in a sealed envelope for review after conduct is completed. Completion of the FSFI and PISQ-IR surveys is optional.
 
Subjects that complete the study will be asked to participate in an optional post study interview with the Study Director and a marketing professional to better understand the subjects' experience using the device. The interview is optional.

Blinding:	Unblinded
Number of Subjects:	Up to 25 subjects meeting inclusion/exclusion criteria at Screening visit will return to the clinic to participate in the treatment phase of the study.
Study Treatment:	/leva Incontinence System™
Key Assessments:	
The following analyses will be performed:
 
Efficacy:
 
• /leva device angle measurements• Survey evaluations of incontinence including:
○ Urinary Incontinence Distress Inventory (UDI-6)○ Incontinence Impact Questionnaire (IIQ-7)

	
○ Patient's Global Impression of Severity (PGI-S)○ Revised Urinary Incontinence Scale (RUIS)○ Patient's Global Impression of Improvement (PGI-I)○ Clinician's Global Impression of Improvement (CGI-I)○ Voiding diary 
Safety and Tolerability:
 
○ Subjects will be monitored for adverse events and serious adverse events.
--	--

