4 STUDY EVENTS FLOW CHART

Study Procedures	Screen	Training Visits	Week 3	Week 6 Visit	End of Study/Early Termination
Visit →	1**	2-30	11	26	31
Inclusion/Exclusion Criteria	X				
Informed Consent	X				
Demographic data	X				
Medical History	X				
Height/Weight	X				
Urine Pregnancy Test	X				
Oral alcohol/Urine Drug Screen	X				
AE Monitoring		X	X	X	X
Concomitant Medication	X	X	X	X	X
Survey: MESA	X				
Surveys: UDI-6, IIQ-7, PGI-S, RUIS	X	X weekly	X	X	X
Surveys: FSFI, PISQ-IR (optional)	X				X
Patient's & Clinical Global Impression-Improvement			X	X	X
Voiding Diary	X		X		X
leva Training	X	X	X	X	
leva Testing/Angle Measurements	X	X* visits 6, 16 & 21	X*	X*	X*
Interview subject about experience using the device (optional)					X

*Preferably on Mondays

** Screening activities can be conducted over 1-2 visits

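### The only baseline voiding diary may be recorded after leva Training has begun, with prior exposure that can differ between subjects

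*Combined protocol and SAP*

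**What the plan says.** Section 7.2 lists the voiding diary among the efficacy endpoints. The flow chart (Section 4) schedules it at Screen, Week 3 and End of Study/Early Termination only. Section 9 agrees: its weekly and 6-week lists omit the diary.

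Under the Screening visit, Section 9 describes a 24-hour diary "to be taken home and completed within the first week of participation". The same visit includes training: "The subject will train for 2 ½ minutes using the" leva device. On the visit's length it says "This visit may be conducted in one to two visits, as needed", and the flow chart footnote agrees: "Screening activities can be conducted over 1-2 visits".

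Section 8.4.1 sets the regimen: "Subjects will train twice daily for 6 (up to 8 weeks) using the" device. The Synopsis places this after Screening: eligible subjects "will return to the clinic to participate in the treatment phase of the study". For Visits 2 to 30, Section 9 gives "Frequency: once a day 5 days a week".

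No section defines when participation starts, states the interval from Screening to Visit 2, or requires the diary to come before training. Section 10.1 defers the statistical methods to the Clinical Study Report, so neither a diary baseline nor the handling of a late diary is specified.

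**The concern.** Section 10.1.1 makes this a single-arm study with within-subject comparison. Change in the diary is then only as good as its baseline, and no control group shares the same baseline error. If some subjects fill in the diary before any training and others after a week of it, the baseline means different things for different subjects, and the error need not be a constant shift. With at most 25 subjects and one recorded day each, this cannot be diagnosed afterwards unless the diary date and the start of training are captured.

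**Working it through.** The plan gives no figure to reproduce. The check is one of scheduling, followed by an illustration.

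**1. Is there another baseline diary?** No. The flow chart and Section 9 agree on three time points, and the second is Week 3.

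**2. How many sessions can come before it?** The inputs are one session at Screening (Section 9), two a day in the treatment phase (Section 8.4.1), and a diary window of up to 7 days (Section 9). Let *d* be the day after Screening on which the diary closes and *v* the day twice-daily training starts. The documents do not give *v*. Sessions up to the close of the diary are 1 + 2 × max(0, *d* − *v*).

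- Window counted from Screening, *d* = 7: *v* = 1 gives 1 + 2 × 6 = 13; *v* = 3 gives 1 + 2 × 4 = 9; *v* = 7 or later gives 1.
- Window counted from Visit 2, with twice-daily training starting there: 1 + 2 × 7 = 15.
- Split screening with the diary completed before the training part: 0.

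The diary covers 24 hours, so about two of the 15 sessions fall inside the recorded day and about 15 − 2 = 13 precede it. The range is therefore 0 to roughly 13–15.

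**3. What might that do to the estimated change?** The documents contain no response-time data, so a shape has to be assumed. If response is linear in training time, the share of change missed is training days before the diary divided by training days to the end of study, both counted from the same start. With five visits a week and test visits "Preferably on Mondays", Visit 31 falls (31 − 1)/5 = 6 weeks, or 42 days, after Visit 1.

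| Case (assumed linear) | Share missed |
|---|---|
| 7 training days, 6-week course | 7/42 = 16.7% |
| Training from the day after Screening, diary on day 7 | (7 − 1)/(42 − 1) = 6/41 = 14.6% |
| Training from day 3, diary on day 7 | (7 − 3)/(42 − 3) = 4/39 = 10.3% |
| 7 training days, 8-week course | 7/56 = 12.5% |
| No effect in week 1 | 0 |

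**4. How far does this depend on the assumed shape?** Almost entirely. With an early-saturating response, 1 − exp(−*t*/τ), a day-7 diary misses (1 − exp(−7/τ))/(1 − exp(−42/τ)) of the day-42 change: 28% for τ = 28 days and 63% for τ = 7 days. If symptoms first worsened by, say, 10% of the final change, improvement would be overstated by 10%. All these inputs are assumptions.

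**The case against.** The strongest case against the point is that nothing shows a few days of training alter a one-day diary at all. The consequence is also limited. UDI-6, IIQ-7, PGI-S, RUIS and the leva Test have Screening values without the take-home window. No primary endpoint is named, no decision rule rests on the diary, and the sample size has no statistical basis. All of this stands. It limits the priority but does not remove the timing gap: a site that follows the text exactly can still obtain a baseline recorded after training.

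A reader might infer three stronger claims that the documents do not support:

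- *That twice-daily training starts on the Screening day, so every baseline follows many sessions.* The Synopsis and Section 8.1 tie the regimen to the treatment phase, and no section describes home training before Visit 2. Split screening or prompt completion can give an untrained or nearly untrained baseline.
- *That improvement will be understated.* This requires an early benefit. The direction could be nil or reversed.
- *That up to half of the Week 3 change is lost.* This takes 7/14 = 50%, with Visit 11 at (11 − 1)/5 = 2 weeks. If training starts the day after Screening, a consistent time origin gives 6/13 = 46%. Either figure needs the latest permitted diary, full adherence, a linear response and a Week 3 visit at 14 days, although Section 9 says 3 weeks.

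**Conclusion.** The point holds as a minor design weakness. The timing gap is certain from the text: the only baseline diary may follow 0 to roughly 13–15 training sessions, and the number can differ between subjects. That this can bias diary change follows from the within-subject design. The direction and size of the bias cannot be determined from the documents. The figure of roughly 15% to 17% of a 6-week change is an illustration that rests on a linear response and a diary after about one week of training; it is zero if the first week has no effect. The issue is confined to the diary.

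**What to change.** In Section 9, and as a note to the Screen diary in the flow chart, replace the one-week window with wording such as: *When screening is split over two visits, the baseline voiding diary is completed before the first leva Training session. When screening is done in one visit, it is completed and returned by Visit 2, before any further leva Training.* Prior exposure is then none, or at most the single Screening session.

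Record the diary date and the date of first leva Training on the CRF. Take the number of earlier sessions from the device log, which Sections 6 and 8.4.2 say is kept. In Section 10.1, state that late diaries are kept and flagged, and that diary change is reported with and without them where numbers allow. With at most 25 subjects one group may be very small; in that case report the spread of session counts instead.

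The cost is two CRF date fields, a tighter return deadline and possibly some additional second screening visits. With one-visit screening, a full 24-hour record must fit between Screening and Visit 2. Splitting screening for everyone is not required. It would add about 25 visits to 25 × 31 = 775 (25/775 = 3.2%), and more if some subjects prove ineligible only at the second visit, since inability to tolerate the device is an exclusion (Section 8.3.2, item 17). The change concerns diary timing and reporting only; no change to the training regimen is proposed.

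### Are the Week 3 and Week 6 assessments placed a week too early, at Visits 11 and 26?

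*Combined protocol and SAP*

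**What the plan says.** Section 9 (Study Procedures) gives the rate of supervised training for Visits 2 to 30 as "Frequency: once a day 5 days a week". It then describes two intermediate assessments by time alone, without visit numbers: "At 3 weeks: The subjects will be asked to perform a series of 5 exercises (leva Test" and, in a separate block, "At 6 weeks: The subjects will be asked to perform a series of 5 exercises (leva Test". End of Study has its own block after these.

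The flow chart in Section 4 heads its last three columns "Week 3 Week 6 Visit End of Study/Early Termination" and numbers its columns "Visit → 1 2-30 11 26 31". Week 3 is therefore Visit 11, the Week 6 Visit is Visit 26, and End of Study is Visit 31. The remaining post-screening leva Tests are at Visits 6, 16 and 21. A footnote prefers Mondays for the post-screening tests, and Section 9 likewise schedules testing "Once a week, preferably Mondays, during the about 6-8 week study period".

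On the starting point, Section 9 says of screening: "This visit may be conducted in one to two visits, as needed". No interval to Visit 2 is given. Visit 1 includes a baseline leva Test and a training session. Sections 8.1 and 8.4.1 give a six-week course that may run to eight weeks.

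**The concern.** Read plainly, an assessment at 3 weeks takes place once three weeks have passed. At five visits a week, ten visits before Visit 11 is two weeks, and 25 visits before Visit 26 is five. Both labels then overstate training time by a week. On the elapsed reading the 6-week assessment would fall on Visit 31, which Section 9 treats as a different visit with different content. The 3-week assessment would fall on Visit 16, where the chart has no PGI-I, CGI-I or voiding diary.

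Subjects are their own controls (Section 10.1.1), so the amount of training behind each measurement matters when change is interpreted. If site staff worked from the Section 9 headings and the report from the flow chart, the same assessment could be collected at one time and described as another. A result labelled 6 weeks might also be taken as the effect of the full course when five supervised visits were still to come.

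**Working it through.** **Inputs.** Five supervised visits a week (Section 9). Visits 11, 26 and 31 for Week 3, Week 6 and End of Study, and tests also at Visits 6, 16 and 21 (Section 4). Preferred test day Monday (Sections 4 and 9). Course of 6 weeks, up to 8 (Sections 8.1 and 8.4.1).

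**Step 1: reproduce the chart's labels.** In an unbroken five-a-week sequence, a Monday test at Visit 6 puts Visits 2 to 5 on the Tuesday to Friday before it. Visit 1 then takes that week's Monday slot. The ordinal week of visit v is floor((v − 1)/5) + 1:

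| Visit | Ordinal week | Day | Weeks after Visit 1, (v − 1)/5 |
|---|---|---|---|
| 6 | 2 | Monday | 1.0 |
| 11 | 3 | Monday | 2.0 |
| 16 | 4 | Monday | 3.0 |
| 21 | 5 | Monday | 4.0 |
| 26 | 6 | Monday | 5.0 |
| 31 | 7 | Monday | 6.0 |

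Visits 11 and 26 open weeks 3 and 6, as the headings say. Visits 1 to 30 make 6 × 5 = 30 sessions, the six-week course, and Visit 31 closes it at six elapsed weeks.

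**Step 2: try the elapsed reading.** Three elapsed weeks is visit 1 + 3 × 5 = 16. Six is visit 1 + 6 × 5 = 31. The second coincides with End of Study. Section 9 describes the two separately: training follows the test in the 6-week block, while End of Study has no training and adds the diary and the optional FSFI and PISQ-IR. The elapsed reading therefore does not fit the plan's own structure at the nominal rate.

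**Step 3: try a different anchor.** If screening came earlier and Visit 2 fell on a Monday, Visit 11 would be 11 days after Visit 2 (11/7 = 1.57 weeks, Friday of week 2) and Visit 26 would be 32 days after it (32/7 = 4.57 weeks, Friday of week 5). All six test visits would then be Fridays, against the stated preference. Nothing forbids this start, but the text points away from it.

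**Step 4: size of the ambiguity.** It is one week at each label. Before Visit 11 there are 10 of 30 supervised visits (33%), against 15 of 30 (50%) after three elapsed weeks. Before Visit 26 there are 25 of 30 (83%), against 30 of 30 (100%).

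**Step 5: what depends on it.** Section 7.2 lists endpoints with no time point. Section 10.1 leaves the methods to the Clinical Study Report. The efficacy population in Section 10.1.2 asks for a leva Test and any post-screening efficacy measurement, at no particular week. No defined quantity changes with the reading.

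**The case for a change.** The best case for acting is that the plan never states the counting rule. Screening can take two visits, the gap to Visit 2 is open, and someone reading only Section 9 would naturally take six weeks as time elapsed. One sentence would settle it. This stands as a remark on wording: no section defines the week labels or their anchor visit.

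The consequences claimed for it are weaker.

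- **Timing of collection.** Section 9 itself points to the flow chart for the procedures at each visit. The chart places PGI-I and CGI-I at Visits 11, 26 and 31, and the diary at screening and Visits 11 and 31. Staff have numbers to follow.
- **Short gap between diaries.** With Visit 11 on day 14 and a baseline diary as late as day 7, the gap could be 14 − 7 = 7 days. That comes mainly from the allowance for the baseline diary, "to be taken home and completed within the first week of participation", and would remain under any definition of week 3.
- **Number of tests.** Weekly testing over eight weeks might suggest up to eight tests against the chart's six after screening. Section 8.1 gives the extra time for scheduling problems, menstrual periods and vacations, which reads as pauses within the same 31 visits. A shortfall is not shown.
- **Stretching to eight weeks.** Two weeks of pauses would put Visit 11 anywhere from 2 to 4 weeks and Visit 26 from 5 to 7. That spread comes from the eight-week allowance, and redefining the labels would not narrow it.

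**Conclusion.** No change to the plan follows. The arithmetic behind the concern is right: at the nominal rate, Visits 11 and 26 fall 2.0 and 5.0 weeks after Visit 1. What it shows is an undefined time label, with a schedule that is coherent when weeks are counted ordinally. The discrepancy is one week at two intermediate assessments. It touches no defined endpoint, analysis population or planned test, and it leaves the Visit 31 result alone.

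This rests on three assumptions: Visit 1 occupies the Monday slot of the first week, as the Monday preference for tests implies; sites work from the visit numbers in the flow chart; and extensions towards eight weeks are pauses within the 31 visits. If the first fails, the ordinal labels can also slip, but the visit numbers still identify each assessment. An analyst who tabulates by visit number will describe the data correctly without any amendment. This conclusion takes no view on how long or how often subjects should train.
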